### 5.4 Study drug administration

Regorafenib (or placebo) is administered as monotherapy during the study. For adults on the study, the starting dose is 160 mg daily for 3 weeks on, 1 week off, taken in the morning with a low-fat meal each day.

The medication should be taken within 8 hours of the same time each day, otherwise should be marked as a missed dose. One cycle is 28 days.

For adults, four 40 mg regorafenib or placebo tablets should be taken in the morning with approximately 8 fluid ounces (240 mL) of water after a low-fat (< 30% fat) breakfast. Some examples of low-fat breakfasts are:

- Two slices of white toast with 1 tablespoon of low-fat margarine and 1 tablespoon of jelly and 8 ounces (240 mL) of skim milk (approximately 319 calories and 8.2 g of fat).
- One cup of cereal, 8 ounces (240 mL) of skim milk, one piece of toast with jam (no butter or marmalade), apple juice, and one cup of coffee or tea (2 g fat, 17 g protein, 93 g of carbohydrate, 520 calories).

The medication will be taken in a similar fashion in pediatric patients (< 18 years). ... Pediatric patients on trial will receive tablets according to the dosing table below (Table 5.4). The starting dose is 82 mg/m^2 daily with the same 3 week on, 1 week off schedule as for adult patients. The regorafenib dose will be rounded to the nearest 20 mg and capped at 160 mg as with adult patients. The lowest permissible dose is 20 mg. The minimum body surface area to participate is 0.65m^2 and minimum weight is 15 Kg. (33 lbs.)

Table 5.4 – Pediatric Doses

	BSA > 0.65m 
Dose level 0 (standard starting dose)	82 mg/m  oral daily

For dose modifications, for adult and pediatric patients, refer to tables in Section 6 of the protocol.

Patients, or their guardians, should be instructed to record daily regorafenib or placebo dose on the Study Drug diary which will be provided to them (Appendix C).

## 5.5 General Concomitant Medication and Supportive Care Guidelines

All medication that is considered necessary for the subject's welfare, and which is not expected to interfere with the evaluation of the study treatment, may be given at the discretion of the investigator. All medications taken within 2 weeks prior to the start of the study and during the study must be recorded in the subject's source documentation, including start/stop dates, dose frequency, route of administration, and indication. Specific caution should be taken when considering or administering a concomitant medication that is metabolized by the cytochrome enzymes CYP2C8, CYP2B6 and CYP2C9. Such concomitant medications should be avoided, if possible.

Co-administration of a strong CYP3A4 inducer (rifampin) with a single 160 mg dose of regorafenib decreased the mean exposure of regorafenib, increased the mean exposure of the active metabolite M-5, and resulted in no change in the mean exposure of the active metabolite M-2. Avoid concomitant use of regorafenib with strong CYP3A4. A listing of strong CYP3A4 inducers is provided in **Appendix D**.

Co-administration of a strong CYP3A4 inhibitor (ketoconazole) with a single 160 mg dose of regorafenib increased the mean exposure of regorafenib and decreased the mean exposure of the active metabolites M-2 and M-5. Avoid concomitant use of regorafenib with strong inhibitors of CYP3A4 activity. A listing of strong CYP3A4 inhibitors is provided in **Appendix D**.

Permitted concomitant therapy includes:

- Standard therapies for concurrent medical conditions
- Supportive care for any underlying illness
- Hematopoietic growth factors: subjects are permitted to take chronic erythropoietin. If a patient develops neutropenia, patients should have doses reduced, and not use growth factors such as filgrastim to artificially elevate the neutrophil count. Use of pegfilgrastim or related growth factors for an episode of febrile neutropenia is permitted
- Treatment with nonconventional therapies (such as acupuncture), and vitamin/mineral supplements are permitted provided that they do not interfere with the study endpoints, in the opinion of the investigator
- Bisphosphonates

- Subjects who are therapeutically treated with an agent such as warfarin or heparin will be allowed to participate provided that their medication dose and INR/PTT are stable, as determined by the investigator.

The following are **not** permitted while the patient is on study:

- Other investigational treatment during or within 14 days (or 5 half-lives, whichever is longer) before starting study treatment
- Radiation therapy: any need for radiation therapy will be defined as clinical (if not radiographic) worsening of disease, and represent a progression event
- Systemic antitumor therapy, including cytotoxic therapy, signal transduction inhibitors, immunotherapy, and hormonal therapy
- Bone marrow transplant or stem cell rescue
- Subjects taking **narrow therapeutic index medications** should be monitored proactively (e.g. **warfarin, phenytoin, quinidine, carbamazepine, phenobarbital, cyclosporine, and digoxin**). Warfarin is metabolized by the cytochrome enzyme CYP2C9 and warfarin levels may be especially affected by regorafenib
- Use of any herbal remedy (e.g. St. John's Wort [*Hypericum perforatum*]).

## 5.6 Duration of Therapy

Treatment may continue until one of the following criteria applies:

- Disease progression as defined by RECIST 1.1
- Greater than 28 days have elapsed since the last dose of study drug
- Patient decides to withdraw from the study during the treatment phase of the study
- Patient decides to withdraw from the study during the follow up phase after completion of treatment on the study
- General or specific changes in the patient's condition render the patient unacceptable for further treatment in the judgment of the investigator.

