### **5. TREATMENT PLAN**

#### **5.1 Agent Administration**

**Cohorts A and B:** patients with liposarcoma or osteosarcoma will be randomized 1:1 to receive regorafenib or placebo. Crossover of the placebo group is permitted if patients still meet all entry criteria to continue on treatment. (Accrual completed as of amendment 5)

**Cohort C:** patients with Ewing sarcomas will all receive regorafenib from the start of the study. (Accrual completed as of amendment 5)

**Cohort D:** patients with rhabdomyosarcoma (fusion-positive alveolar, embryonal, and fusion-negative alveolar) will all receive regorafenib from the start of the study

**Cohort E:** patients with mesenchymal chondrosarcoma will all receive regorafenib from the start of the study

In all cases the length of one cycle of therapy is 28 days (3 weeks on, 1 week off). If a patient experiences toxicity and is not due to resume therapy until the 1 week of the cycle off treatment, the subsequent cycle of therapy may start after a minimum of 1 week off regorafenib.

Example 1: A patient experiences toxicity at the day 8 visit of a cycle and treatment is held until day 15. After resuming treatment from day 15 until day 22, the patient is off treatment from days 22-28, and starts again on day 29, which is day 1 of the new cycle of therapy.

Example 2: A patient experiences toxicity at day 17 and treatment is held through day 24, which is after the expected end of treatment that cycle on day 22. The patient may resume therapy with a new cycle of therapy as early as day 25, or may stay off therapy through day 28, resuming treatment cycle day 29/day 1 of the new cycle.

Conversely, imaging studies will be performed as outlined in the protocol and no changes in the scheduled scans are permitted. However, patients with clinical deterioration may have imaging studies earlier than scheduled, which may take the patient off study earlier than expected.

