## 5.8 Criteria for Removal from Study

Patients will be removed from study when any of the criteria listed in Section 5.6 applies. The reason for study removal and the date the patient was removed must be documented in the eCRF including death or lost to follow up.

Subjects **must be withdrawn from the trial** (treatment and procedures) for the following reasons:

- Subject withdraws consent from study treatment and study procedures. A subject must be removed from the trial at his/her own request or at the request of his/her legally acceptable representative. At any time during the trial and without giving reasons, a subject may decline to participate further. The subject will not suffer any disadvantage as a result
- Pregnancy. Pregnancy will be reported as an SAE. (Note: subjects who have been withdrawn from treatment with study drug because of pregnancy should not undergo CT scans [with contrast]/MRI or bone scans while pregnant.)
- If, in the investigator's opinion, continuation of the trial would be harmful to the subject's well-being
- Subject is lost to follow-up
- Death.

Subjects **may be** withdrawn from the study for the following reasons:

- The subject is non-compliant with study drug (regorafenib or placebo), trial procedures, or both; including the use of anti-cancer therapy not prescribed by the study protocol
- Severe allergic reaction to regorafenib (such as exfoliative erythroderma or Grade 3 or 4 hypersensitivity reaction)
- Development of a second cancer
- Development of an intercurrent illness or situation which would, in the judgment of the investigator, significantly affect assessments of clinical status and trial endpoints
- Deterioration of WHO performance status to 4
- Use of illicit drugs or other substances that may, in the opinion of the investigator, have a reasonable chance of contributing to toxicity or otherwise skewing trial result.

Any subject removed from the trial will remain under medical supervision until discharge or transfer is medically acceptable. In all cases, the reason for withdrawal must be recorded in the eCRF and in the subject's medical records.

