## **6.2 Management of toxicity (other than hand-foot skin reaction, hypertension and LFT abnormalities)**

The table below outlines dose adjustments for **most hematologic and non-hematologic toxicities related to regorafenib** except hand-foot skin reaction (HFSR) and hypertension and LFT abnormalities.

In addition to these recommended dose modifications, subjects who develop diarrhea (see

Section 6.6), mucositis, anorexia or other events predisposing to fluid loss or inadequate fluid intake should be carefully monitored and rehydrated as clinically necessary. This is in order to minimize the risk of postural hypotension and renal failure.

**Table 6.2 Recommended dose modification for most toxicities, except hand-foot skin reaction, hypertension and ALT/AST/bilirubin**

NCI-CTCAE v 4.03 a	Dose Interruption	Dose Modification b	Dose for Subsequent Cycles
Grade (G) 0-2	Treat on time	No change	No change
G 3	Delay until $\leq$ G 2 c	Reduce by 1 dose level	If toxicity remains < G2, dose re-escalation can be considered at the discretion of the treating investigator. If dose is re-escalated and toxicity ( $\geq$ G3) recurs, institute permanent dose reduction.
G 4	Delay until $\leq$ G 2 c	At a minimum, reduce by 1 dose level.  Strongly consider permanent discontinuation for G4 events such as: gastrointestinal perforation/fistula, severe or life-threatening hemorrhage, reversible posterior leukoencephalopathy syndrome, or wound dehiscence.	

a. G: Grade; NCI-CTCAE = National Cancer Institute - Common Terminology Criteria for Adverse Events, version 4.03
 
b. Excludes alopecia, non-refractory nausea/vomiting, non-refractory hypersensitivity and nonclinical and asymptomatic laboratory abnormalities.
 
c. If no recovery after a 4 week delay, treatment should be permanently discontinued unless subject is deriving clinical benefit and is discussed with the SARC Medical Officer.
			

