**Table 6.3.2 Recommended dose modification for hand-foot-skin reactiona**

Grade of event (NCI-CTCAE v 4.03)	Occurrence	Suggested Dose Modification
Grade (G) 1	Any	Maintain dose level and immediately institute supportive measures for symptomatic relief
G 2	1 st occurrence	Consider decreasing dose by one dose level and immediately institute supportive measures. If no improvement, interrupt therapy for a minimum of 7 days, until toxicity resolves to G 0-1 b, c
	No improvement within 7 days or 2 nd occurrence	Interrupt therapy until toxicity resolves to G 0-1. c When resuming treatment, decrease dose by one dose level b
	3 rd occurrence	Interrupt therapy until toxicity resolves to G 0-1. c When resuming treatment, decrease dose by one dose level. b, d
	4 th occurrence	Discontinue therapy
G 3	1 st occurrence	Institute supportive measures immediately. Interrupt therapy for a minimum of 7 days until toxicity resolves to G 0-1. c When resuming treatment, decrease dose by one dose level. b, d
	2 nd occurrence	Institute supportive measures immediately. Interrupt therapy for a minimum of 7 days until toxicity resolves to G 0-1. c When resuming treatment, decrease dose by one additional dose level b, d
	3 rd occurrence	Discontinue treatment permanently.

a. More conservative management is allowed if judged medically appropriate by the investigator.
 
b. If toxicity returns to G 0-1 after dose reduction, dose re-escalation is permitted at the discretion of the investigator if subject has completed one cycle at reduced dose without recurrence of event.
 
c. If there is no recovery after a 4 week delay, treatment with regorafenib or placebo will be discontinued permanently.
 
d. Subjects requiring > 2 dose reductions should go off protocol therapy.
 
e. The maximum daily dose is 160 mg
		

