
a. Patients requiring a delay of > 4 weeks should will discontinue regorafenib or placebo and stop participation in the study.
 
b. If BP remains controlled for at least one cycle, dose re-escalation is permitted per investigator's discretion.
 
c. Patients requiring > 2 dose reductions should go off protocol therapy.
 
G: Grade
		

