**Table 6.5.1 Recommended measures and dose modification in case of drug-related liver function test abnormalities**

Observed elevations of ALT and/or AST	Occurrence	Recommended measures and dose modification
≤ 5 times upper limit of normal ULN (maximum Grade 2)	Any occurrence	Continue regorafenib or placebo treatment.  Monitor liver function weekly until transaminases return to < 3 times ULN (Grade 1) or baseline.
>5 times ULN to ≤ 20 times ULN (Grade 3)	1 st occurrence	Interrupt regorafenib or placebo treatment.  Monitor transaminases weekly until return to < 3 times ULN or baseline.  Restart: If the potential benefit outweighs the risk of hepatotoxicity, re-initiate regorafenib or placebo treatment, reduce dose by 40 mg (one tablet), and monitor liver function weekly for at least 4 weeks.
	Re-occurrence	Discontinue treatment with regorafenib or placebo permanently.
> 20 times ULN (Grade 4)	Any occurrence	Discontinue treatment with regorafenib or placebo permanently.
> 3 times ULN (Grade 2 or higher) with concurrent hyperbilirubinemia > 2 times ULN		Discontinue treatment with regorafenib or placebo permanently.  Monitor liver function weekly until resolution to < 3 times ULN or return to baseline.  Exception: patients with Gilbert syndrome who develop elevated transaminases should be managed as per the above outlined recommendations for the respective elevation of ALT and/or AST.

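### Sections 5.6 and 5.8 remove a patient more than 28 days after the last dose, but Table 6.2 lets the same patient continue, and the start of the 4-week delay is undefined

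*Combined protocol and SAP*

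**What the plan says.** Section 5.6 (Duration of Therapy) lists the points at which treatment ends. One is "Greater than 28 days have elapsed since the last dose of study drug". Section 5.8 adds: "Patients will be removed from study when any of the criteria listed in Section 5.6 applies". Neither section qualifies the 28-day criterion.

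The dose-modification tables in Section 6 set their own time limits:

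- Table 6.2, footnote c (most toxicities), where the person to be consulted is the Medical Officer: "If no recovery after a 4 week delay, treatment should be permanently discontinued unless subject is deriving clinical benefit and is discussed with the SARC".
- Table 6.3.2, footnote c (hand-foot skin reaction): "If there is no recovery after a 4 week delay, treatment with regorafenib or placebo will be discontinued permanently".
- Table 6.4.1, footnote a (hypertension): "Patients requiring a delay of > 4 weeks should will discontinue regorafenib or placebo and stop participation in the study".
- Table 6.5.1 (liver tests) gives no time limit for a Grade 3 interruption, only a monitoring rule: "Monitor transaminases weekly until return to < 3 times ULN or baseline".

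Section 5.1 sets the dosing rhythm: "In all cases the length of one cycle of therapy is 28 days (3 weeks on, 1 week off"). It also keeps imaging on its planned dates whatever happens to dosing. No passage says whether the 4-week delay runs from the last dose taken or from the next dose due, or whether Section 5.6 or Table 6.2 prevails.

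**The concern.** A site managing a slow recovery has two instructions. For a patient who is benefiting, Table 6.2 provides a route to stay on treatment past 4 weeks, while Sections 5.6 and 5.8 require removal. Sites could follow different sections and both be compliant with part of the protocol.

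The consequence reaches the endpoints because Section 5.8 removes the patient from the study, not only from the drug. Section 9.3 provides an off-study evaluation, with imaging if it has not already been done, and then a phone call at 30 to 45 days. No scheduled scans follow. Under Section 12.1.1, PFS for a patient alive without progression is censored at the last tumour assessment. A toxicity hold can therefore lead to censoring or to a missing landmark status, depending on which section the site applied. The cohorts still described as accruing, D and E, are decided on about 12 patients each, with cut-offs of 3 and 4 patients with disease control (Section 12.2).

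**Working it through.** There is no design figure to reproduce, since no sample size, event count or error rate is involved. The check sets the clauses side by side and counts days.

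**Inputs.** Limit in Section 5.6: more than 28 days since the last dose. Limit in Tables 6.2, 6.3.2 and 6.4.1: a 4-week delay, 4 × 7 = 28 days. Cycle (Section 5.1): 21 days on and 7 off, so the last planned dose is day 21 and the next cycle is due on day 29.

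**1. The Table 6.2 exception.** It operates only once the delay has passed 4 weeks. Whether the delay runs from the last dose or from a later due date, the time since the last dose is then more than 28 days. Section 5.6 has been met, and Section 5.8 removes the patient. The exception cannot be used without breaching both.

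**2. The plain 4-week limit.** Days since last dose at the end of the delay = (start of delay + 28) − day of last dose.

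| Start of the clock | Last dose | Delay ends | Days since last dose | Against Section 5.6 |
|---|---|---|---|---|
| Last dose taken | day 21 | day 49 | 28 | agrees (not more than 28) |
| First missed dose, mid-cycle | day 7 (due day 8) | day 36 | 29 | one day over |
| First missed dose, mid-cycle | day 14 (due day 15) | day 43 | 29 | one day over |
| Planned restart after the off week | day 21 (due day 29) | day 57 | 36 | 8 days over |

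In the last row, Section 5.6 allows a restart up to day 21 + 28 = day 49, which is 49 − 29 = 20 days after the due date.

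**3. Stated consequence.** Table 6.3.2 ends the drug. Table 6.4.1 ends the drug and study participation. Section 5.8 ends study participation for the 28-day criterion.

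**4. Reach into the landmarks.** Scans fall every 8 weeks to week 32.

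- Cohort E is judged at 24 weeks. A patient removed well before then has no scheduled 24-week scan. One patient is 1/12 = 8.3 percentage points, against a cut-off of 4 of 12. Section 12.2 does not say how a patient without that assessment is counted.
- Cohort D is judged at 8 weeks. Week 8 is days 50–56, or days 43–63 with the ±7-day window. Last dose on day 21 means removal from day 50 (50 − 21 = 29), inside week 8, so the off-study scan can supply the status. Last dose on day 7 means removal from day 36, and a scan done then is 7 days before the window opens. Only holds that start early in cycle 1 are exposed.

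**5. Frequency.** The only data in the documents are from the paediatric phase I study (Section 2.4.3). Interruptions there lasted a median of 4 days, range 1–17, excluding the 7-day rest. At the maximum, 7 + 17 = 24 drug-free days. Restart on day 29 + 17 = day 46 is 25 days after the last dose, still inside 28.

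**The case against.** The strongest reply is that most of the text can be read consistently. If the delay runs from the last dose, 4 weeks is exactly 28 days, which is not more than 28, and Tables 6.3.2 and 6.4.1 match Section 5.6. Example 2 in Section 5.1 leans that way: a hold from day 17 through day 24 runs into the off week, and the off-week days count as part of the hold. Table 6.4.1 also agrees with Section 5.8 that exceeding the limit ends participation. This stands. A reader might infer that all three tables contradict Section 5.6 by 20 days against 28. The documents do not support that, because the gap appears only if the clock starts at the planned restart, which no passage says. What remains is that the start is undefined and the answer depends on it.

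It can also be said that the Table 6.2 exception is the more specific rule and should override the general one. That is a possible intention, but nothing in the text says so, and Section 5.8 applies whenever any Section 5.6 criterion is met.

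A third reply is that the event is rare, and this also stands. A reader might take the 65.9% of phase I patients with a dose modification as a sign that long holds are common. That figure covers every kind of modification, and no interruption reported there would by its length have crossed the limit.

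Finally, the loss of scans after removal follows from Section 9.3 whichever limit is chosen. Reconciling the limits settles who is removed. It does not create follow-up imaging for those who are.

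**Conclusion.** The contradiction between Table 6.2 footnote c and Sections 5.6 and 5.8 is established and does not depend on how days are counted: the same patient may continue under one and must be removed under the others. The disagreement over the plain 4-week limit is conditional. It is nil if the clock starts at the last dose, one day if it starts at a missed mid-cycle dose, and 8 days (day 57 against day 49) if it starts at the planned restart after the off week. The tables also differ on whether the patient leaves the drug or the study.

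The exposure is mainly Cohort E's 24-week status, where one patient is 8.3 percentage points of a cohort of about 12. For Cohort D it is limited to holds that begin early in cycle 1. A reader might infer a general threat to Cohort D's decision, but for a hold at the end of cycle 1 the off-study scan falls in week 8 and can serve. Cohorts A, B and C had completed enrolment, so a change has little reach there.

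The documents do not show how often the conflict would arise, and it is probably rare. The case for acting is that the rules conflict as written and are cheap to align. Nothing here shows which limit or stopping rule is right.

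**What to change.** The sponsor should reconcile Sections 5.6 and 5.8 with the footnotes of Tables 6.2, 6.3.2 and 6.4.1, so that the protocol states:

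- one limit;
- one start for the clock, either the last dose taken or the next dose due;
- whether the Table 6.2 benefit exception applies, cross-referenced from Section 5.6;
- whether exceeding the limit ends study drug only, or study participation as well.

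Which limit and which consequence apply is for the sponsor to decide. For patients whom the reconciled text keeps on study, tumour assessments should follow the existing schedule of every 8 weeks to week 32, then every 12 weeks.

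The cost is wording in two sections and three footnotes. The small downside is a few more scheduled scans if the reconciled text keeps more patients on study.
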